# Master Protocol

sporadic, non-classical DBA if a reported mutation is present. A patient can be assigned as having a “probable” diagnosis, with a decreasing degree of certitude if; 3 diagnostic criteria are present along with a positive family history; 2 diagnostic criteria and 3 minor supporting criteria are present; or, a positive family history and 3 minor supporting criteria are evident, even in the absence of diagnostic criteria. Steroid responsiveness is not considered a diagnostic criterion and corticosteroids should not be administered until a diagnosis is made.

If the first three diagnostic criteria are present, but there is no paucity of red cell precursors in the bone marrow and no supporting criteria, the diagnosis of DBA cannot be made. A bone marrow evaluation should be repeated at a later date as red cell marrow hypoplasia may develop after anemia and reticulocytopenia are observed.

The criteria used for diagnosis must be delineated (Appendix A). Prior to enrollment the principal investigator will determine if the patient meets the diagnostic criteria for inclusion in the study.

**9.1.2** The study is restricted to patients who are receiving no DBA specific therapy other than red blood cell transfusions. Patient will remain on his/her transfusion schedule for the duration of this study without any other DBA medications such as therapeutic corticosteroids, anabolic steroids, cyclosporine, etc. to be taken simultaneously or added during the course of this study. Patients must be off of therapeutic corticosteroids or any immunosuppressive therapy for 30 days prior to study enrollment. Hydrocortisone for treatment of adrenal insufficiency will be permitted. Iron chelation medications will be allowed as standard of care for transfused patients.

**9.1.3** Patient should have adequate renal function defined as:

- Creatinine clearance or radioisotope GFR  $\geq 70\text{ml/min}/1.73\text{ m}^2$  OR
- A serum creatinine based on age/gender as follows:

Age	Maximum Serum Creatinine	
	(mg/dL)	
	Male	Female
1 to < 2 years	0.6	0.6
2 to < 6 years	0.8	0.8
6 to < 10 years	1	1
10 to < 13 years	1.2	1.2
13 to < 16 years	1.5	1.4
$\geq 16$ years	1.7	1.4

The threshold creatinine values in this table were derived from the Schwartz formula for estimating GFR utilizing child length and stature data published by the CDC.

**9.1.4** Patient should have adequate liver function defined as:

- Total Bilirubin  $\leq 1.5 \times$  upper limit of normal (ULN) for age, and
- SGPT (ALT)  $< 5 \times$  upper limit of normal (ULN) for age
- Serum albumin  $\geq 2$  g/dL

**9.1.5** Negative pregnancy test if subject is a menstruating female and documentation of agreement to use adequate contraception for at least 28 days before starting the study, while taking the leucine, and for at least 3 months after the last dose of study medication .

# Master Protocol

## **9.1.6** Signed informed consent.

**9.1.7** Registration in the Diamond Blackfan Anemia Registry (DBAR) may be offered but is not required for study enrollment.

## **9.2 Exclusion Criteria**

**9.2.1** Known hypersensitivity to branched chain amino acids

**9.2.2 Diagnosis** of an inborn error of amino acid metabolism disorder

**9.2.3 Prior** hematopoietic stem cell transplantation

**9.2.4 Pregnancy**, or plans to become pregnant during duration of trial

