## 6.4 Contraindications

Hypersensitivity to branched chain amino acids, anuria, and inborn errors of amino acid metabolism, especially those that involve branched chain amino acid metabolism, such as maple syrup urine disease and isovaleric acidemia are contraindications.

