## 6.7 Pregnancy/Lactation

Excessive leucine administration interferes with embryo development in rats. Scientific evidence for the safe use of branched chain amino acids during pregnancy and lactation is not available as there are no human data.

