## 9.0 PATIENT ELIGIBILITY

All clinical and laboratory studies to determine patient eligibility must be performed within 30 days prior to study enrollment unless otherwise indicated. Laboratory values used to assess eligibility must be no older than thirty days at the start of therapy. Laboratory tests need not be repeated if therapy starts within thirty days of obtaining labs to assess eligibility. If a post-enrollment lab value is outside the limits of eligibility, or laboratory values are >30 days old, then the following laboratory evaluations must be re-checked prior to initiating therapy: CBC with differential, bilirubin, ALT (SGPT) and serum creatinine. If the recheck is outside the limits of eligibility, the patient may not receive protocol therapy and will be considered off protocol.

**Important note:** The eligibility criteria listed below are interpreted literally and cannot be waived. All clinical and laboratory data required for determining eligibility of a subject enrolled on this trial must be available in the patient's medical or research record which will serve as the source document for verification at the time of audit.

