### 9.1 Inclusion Criteria

**9.1.1** Transfusion dependent DBA age 2 years and older.

**9.1.1.1** Transfusion dependence is defined as  $\geq 10$  cc/kg or if over 60 kg 2 units of RBC per 28 days averaged over 84 days (3 months) prior to study entry.

**9.1.1.2** Diagnostic and supporting criteria for the diagnosis of DBA as published in British Journal of Haematology (8) and described in table below.

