## 19.0 HUMAN SUBJECT PROTECTION

### 19.1 Rationale for Subject Selection

**19.1.1** This study will be open to all subjects who fully meet the inclusion and exclusion criteria as described in section **9.0**. Epidemiologic data suggests that the gender will be approximately evenly split between males and females as the DBAR has reported the male: female ratio to be 1.03:1.00. DBA has been reported in nearly all ethnicities.

**19.1.2** This study will be listed on:

- [www.clinicaltrials.gov](http://www.clinicaltrials.gov) (NHLBI patient recruitment site)
- [www.dbar.org](http://www.dbar.org) (Diamond Blackfan Anemia Registry site)
- [www.dmaf.org](http://www.dmaf.org) (Daniella Maria Arturi Foundation site)
- [www.dbafoundation.org](http://www.dbafoundation.org) (Diamond Blackfan Anemia Foundation site)

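### Section 6.7 reports no human data on branched chain amino acids in lactation, but Section 9 has no criterion on breastfeeding, and 9.1.5 leaves a related gap in the contraception agreement

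*Combined protocol and SAP*

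**What the plan says.** Section 6.7 of the protocol covers pregnancy and lactation under one heading. It first reports an effect of excessive leucine on rat embryos, then says: "Scientific evidence for the safe use of branched chain amino acids during pregnancy and lactation is not available as there are no human data".

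Section 9.2 lists four exclusions: hypersensitivity to branched chain amino acids, an inborn error of amino acid metabolism, prior stem cell transplantation, and pregnancy "or plans to become pregnant during duration of trial". Breastfeeding is not among them.

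Inclusion 9.1.5 reads in part: "Negative pregnancy test if subject is a menstruating female and documentation of agreement to use adequate contraception". The agreement runs from at least 28 days before the start to at least 3 months after the last dose. Section 12.2.2.6 describes the women to be pregnancy-tested differently, by child-bearing potential, and asks for a test at baseline and every 3 months.

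On how the criteria are used, Section 9.0 states: "The eligibility criteria listed below are interpreted literally and cannot be waived". Section 19.1.1 adds: "This study will be open to all subjects who fully meet the inclusion and exclusion criteria". The age criterion is "Transfusion dependent DBA age 2 years and older", with no upper limit, and Section 10.0 includes both sexes. Sections 8 and 13.0 set dosing at 9 months.

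**The concern.** The protocol's own drug information names lactation as a setting without human safety data, and nothing in the eligibility section follows from that. With literal application and no waiver, a local investigator has no written criterion on which to decline a woman because she is breastfeeding. The person who might be exposed is a nursing infant, who is not a consented subject.

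The wording of 9.1.5 adds a related gap. A woman of child-bearing potential who is not menstruating, as can happen while breastfeeding, falls outside its literal condition. She might then enter without the contraception agreement that other women must give.

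**Working it through.** No arithmetic underlies this point, and the plan gives no figure to reproduce. The check sets the relevant sections side by side.

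**Step 1. Where lactation appears.** Apart from the table of contents, the available text mentions it only in Section 6.7.

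| Section | Pregnancy | Lactation |
|---|---|---|
| 6.4 Contraindications | not listed | not listed |
| 6.7 Pregnancy/Lactation | rat embryo effect; no human data | no human data |
| 9.1.5 Inclusion | test and contraception | silent |
| 9.2.4 Exclusion | excluded, present or planned | silent |
| 12.2.2.6 and 13.3 | tested at baseline, then every 3 months (13.3 marks visits 0, 3 and 6 months) | silent |
| 15.0 Withdrawal | not listed | not listed |

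**Step 2. Can such a woman enter?** Adult women are within the age and sex range. She must still meet every other criterion: transfusion dependence, diagnosis, renal and hepatic function, no other DBA therapy, and consent. If she does, nothing in Section 9 excludes her for breastfeeding, and Sections 9.0 and 19.1.1 then point to entry. Dosing lasts 9 months.

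**Step 3. Is this stated as a choice?** No available section says that breastfeeding women are meant to be eligible, or gives a reason.

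**Step 4. The two descriptions of women.** Section 9.1.5 speaks of a menstruating female and 12.2.2.6 of a female with child-bearing potential. For a woman in the second group but not the first:
- Pregnancy test: covered, because 12.2.2.6 requires it at baseline.
- Exclusion if pregnant: covered, because 9.2.4 does not depend on menstruation.
- Contraception agreement: not covered if the condition in 9.1.5 governs both parts of the sentence. The other reading, that the agreement binds every subject, closes the gap but would apply it to males and to children from age 2.

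**Step 5. Size.** The documents give no frequency. Assuming 0 to 1 breastfeeding woman among the maximum of 50 subjects, the share is 0/50 = 0% to 1/50 = 2%.

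**The case against.** The strongest reply is that Section 6.7 does not put the two states on the same footing. The rat embryo finding concerns pregnancy only, and only the sentence on absent human data covers both. Excluding pregnancy while saying nothing about lactation can therefore be a coherent choice. Section 6.4 supports this: its list begins "Hypersensitivity to branched chain amino acids, anuria, and inborn errors of amino acid metabolism" and does not include lactation. This stands. A reader might infer that 6.7 treats pregnancy and lactation alike and that 9.2.4 contradicts it, but the text supports only an unexplained mismatch.

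The protocol also describes oral leucine as low in toxicity. Section 3.0 cites its GRAS status, and Section 6.5 cites a study of a branched chain amino acid drink that provided 24 g/day of leucine without reported adverse effects. At an assumed 1.7 m², the trial dose is 2100 mg/m² × 1.7 m² = 3570 mg, or about 3.6 g/day. None of this is lactation data, but it may be a basis for allowing breastfeeding. The protocol does not say so. The documents contain no evidence of harm to infants, and this point claims none.

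Three further inferences are tempting:
- **That nothing would detect or record an infant's exposure.** This cannot be asserted. The consent form, screening checklist, enrollment form and case report form (Appendices B, C, D and G) are not in the available text, and any of them could ask about breastfeeding. Section 17.2 also extends the research monitor's review to problems involving risk to people other than subjects. If an appendix does address breastfeeding, Section 9 would still need to match it.
- **That the deficiency objective (4.2.1) would be distorted.** Nothing in the documents supports this. One subject of 50 moves a proportion by at most 2 percentage points, and Section 16.5 accepts a half-width of up to 13.9 points.
- **That a non-menstruating woman escapes pregnancy testing.** She does not, because 12.2.2.6 covers her.

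**Conclusion.** The point holds as a gap in eligibility wording. Section 6.7 says that human safety data in lactation are lacking, no criterion in Section 9 addresses breastfeeding, and no available section explains the silence. The statement in 6.7 is about branched chain amino acids as a class. Applying it to leucine is fair, because Section 6.0 names leucine as one of the three.

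The contraception part is narrower. It rests on reading the condition in 9.1.5 as governing the whole sentence, and it concerns women of child-bearing potential who are not menstruating.

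The expected number is very small: 0 to 1 of 50 by assumption. Sample size, endpoints and analysis are unaffected. The case for acting is that the person potentially exposed has not consented and the correction is cheap.

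**What to change.** 1. Reconcile 9.2.4 with 6.7. Either add current or planned breastfeeding during the trial to 9.2.4 and to the Eligibility Screening Checklist (Appendix C), or state in 6.7 the basis on which breastfeeding women may take part. Which of the two is the sponsor's decision.
2. In 9.1.5, replace the menstruation condition with the child-bearing-potential term already used in 12.2.2.6, and word the sentence so that it is clear to whom the contraception agreement applies.
3. Check that Appendices B, C, D and G agree with the wording chosen.

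The cost is a few words in 9.1.5, in the checklist and in 9.2.4 or 6.7, with the usual amendment approvals. The only downside is the possible loss of a very few subjects, 0 to 1 of 50 under the same assumption.

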## **10.0 SUBJECT RECRUITMENT**

Patients with Diamond Blackfan anemia are generally cared for at larger academic centers because of the rarity of the disease and the need for transfusion therapy in about half of the patients. The PI of this protocol is a known clinical researcher in the DBA field. [name] directs the Comprehensive Diamond Blackfan Anemia Clinical Care Center and the Diamond Blackfan Anemia Surveillance and Awareness Program housed at the Steven and Alexandra Cohen Children's Medical Center of New York. Through these efforts many physicians and patients/parents of patients often contact [name] and the DBA Study Coordinator [name] for information about DBA. Contact is made via telephone, fax and/or e-mail. Recruitment for this study can occur via three methods:

- 1) The PI and Co-Investigators' institutions will be recruiting patients by word of mouth as they have multiple DBA patients whom they care for that are eligible for enrollment. Many of these patients have already shown interest in this study.
- 2) Other physicians caring for DBA patients throughout the country that are interested in the study may directly contact the PI and/or the Study Coordinator. The protocol and consent will be sent to these physicians. IRB approval will be obtained at these institutions. The patient will be enrolled onto the study if they meet the eligibility requirements.
- 3) Subjects/Parents of subjects may contact the PI or Study Coordinator directly. The patient will be referred to a local institution that has an IRB-approved protocol. If one does not exist, the patient will be instructed to have his/her physician contact the PI and/or Study Coordinator to obtain the protocol. The PI and/or Study Coordinator will assist the physician to obtain IRB approval and enroll the patient if the patient is eligible.

This study will be announced via the Diamond Blackfan Anemia Foundation website ([www.dbafoundation.org](http://www.dbafoundation.org)), the DBA Yahoo Group chat room, the Daniella Maria Arturi Foundation website ([www.DMAF.org](http://www.DMAF.org)), the DBAR website ([www.dbar.org](http://www.dbar.org)), and the Diamond Blackfan Anemia Surveillance and Awareness Program Facebook site. As the DBA community is a close-knit one with an excellent network, recruitment is expected to be accomplished rapidly through word of mouth.

This study is funded for 50 subjects. We expect to recruit 50-60 subjects of which the first 50 eligible patients will be enrolled. Our target population is the DBA patient community, aged 2

# Master Protocol

years and older, males and females alike. This disease is noted in all racial and ethnic groups so all are included. The consent will be available in English only at this time. For non-English speaking subjects, a certified oral interpreter service will be used for obtaining informed consent.

## 11.0 TREATMENT OF SUBJECTS

This study will be a multi-institution study. Institutions must enroll patients directly on this protocol. Patients will also be offered enrollment on the Diamond Blackfan Anemia Registry (DBAR - see section 11.3).

### 11.1 Informed Consent, Subject Enrollment and Eligibility Screening

The process of informed consent, eligibility screening and enrollment is as follows:

- a. The local PI or his/her designee calls the Central Study Coordinator to verify that the study is still accruing subjects.
- b. The local PI will obtain informed consent from the subject or his/her parents/legal guardian for enrollment into the study.
- c. Once informed consent is signed, the local PI will call/e-mail the Coordinating Center and a participant identification number will be assigned by the Central Study Coordinator.
- d. Screening of the patient for eligibility will proceed with completion of the Eligibility Screening Checklist which will be forwarded to the Coordinating Center.
- e. The local PI will be informed of the patient's eligibility by fax and/or e-mail within 24 hours of receipt of the Eligibility Screening Checklist or by the next business day.
- f. Participant enrollment will then proceed with assignment of the leucine dose. The Enrollment Form will be submitted by local PI as required.
- g. This process will be repeated until 50 subjects are enrolled. Patients found to be not eligible after screening will be deemed 'screen failures'.

#### 11.1.1 Current Study Status

Local investigators or their designee must contact the Primary Institution ([name]) to determine if the study is currently open for accrual. This is to ensure that no more than 50 subjects are enrolled on the study. Once 50 subjects are enrolled, excluding the 'screen failures', a memo will be sent out to all participating institutions that accrual has been reached.

#### 11.1.2 Informed Consent/Assent (Appendix B)

A signed informed consent document will be obtained prior to entry onto this study. The consent documents may be mailed or e-mailed for potential subjects to review, however the actual consent process will take place in person. The principal investigator and/or sub investigator will obtain consent after the patient and/or patient's parent/legal guardian are informed of the investigational nature and research objectives of the trial, the procedures and treatments involved and their attendant risks and discomforts as well as potential alternative therapies. The local PI and his/her designees will be well versed in this study. There is no urgency in the start of this medication for DBA patients. Patients and their guardians will be allotted ample time to review the study risks/benefits before signing consent. It will be allowable to have those patients not treated at the consenting institution to take the consent home to discuss with their treating hematologist, only after discussing the study and going through the consent process with appropriate documentation. If they decide to enroll, they may mail the consent back to the

# Master Protocol

coordinating center. It will not be uncommon to discuss the study with the patient and consent them at their next transfusion visit 3-4 weeks later. Any and all questions will be answered regarding the study and the required tasks. The informed consent and assent will be signed according to institutional guidelines. Documentation of the informed consent will be maintained in the subject's research chart.

**11.1.2.1** Consent will be obtained from the subject himself/herself, or, in the case of a minor, from the parent or legal guardian. Subjects ages 7-11 and 12-17 (or as determined by the local IRB) who are able to read and understand an assent will be asked to sign a simplified document, along with their parent or guardian signing the standard consent form. Minors who turn 18 while still active in the study will be consented as adults. These may be mailed, as a face to face reconsent may not be feasible for those treated at outside facilities. A copy will be given to the subject/subject's legal guardian by the person obtaining the consent.

**11.1.2.2** The original consent form will be kept in the subject's chart at the subject's local institution and will be available for review if needed by a monitoring body.

**11.1.2.3** If at any time during study participation new information becomes available relating to risks, adverse events, or toxicities, this information will be provided orally or in writing to each enrolled subject and re-consent obtained as appropriate. Documentation will be provided to the IRB and if necessary, the informed consent amended to reflect relevant information.

## **11.1.3 Subject Identification**

Once the subject/parent of patient/legal guardian has signed consent, the local institution will call the Coordinating Center ([name]) to obtain participant identification (ID) number from the Central Study Coordinator. A confidential copy will be sent to the local institution with the subject's ID for confirmation. A participant identification number will be assigned to identify the subject to that investigator and institution and will be used in all future communications with the site. This is to assure that no two possible subjects are enrolled simultaneously.

### **11.1.3.1 *Participant Identification Number (PIN)***

Each subject registered will be assigned a unique participant identification number. This PIN will consist of two parts: the first two digits will identify the local institution who is registering the subject, and the three last digits will number the subjects from that institution consecutively. The funding allows for a total of 17 possible institutions so the first two digits will range from 01 (the Coordinating Center) to 17. For example, PIN 01-001 will indicate the first subject on study, which in this case would have been enrolled by the Coordinating Center. Each potential patient will be assigned an ID once the consent has been signed. If the subject does not meet the eligibility criteria once screening occurs then that number will be skipped.

## **11.1.4 Eligibility Screening**

Diagnostic or laboratory studies performed exclusively to determine eligibility for this study must be done only after obtaining written informed consent. Eligibility is then verified by meeting the criteria listed in the Eligibility Screening Checklist (Appendix C). Studies or procedures that were performed for clinical indications (not exclusively for eligibility for this study) may be used for baseline values if the studies were done within thirty days of when the informed consent was obtained. Before the subject can be enrolled, the responsible institutional investigator must sign and date the completed Eligibility Screening Checklist. A signed copy of the Eligibility Screening Checklist will be faxed to the Coordinating Center ([name]). The fax should be sent to the attention of the Central Study Coordinator and must include the

